7. **Required HIPAA Authorization:** If the research involves the creation, use or disclosure of protected health information (PHI), separate subject authorization is required under the HIPAA Privacy Rule. Indicate which of the following forms are being provided:

- Compound Consent and Authorization form
 HIPAA Research Authorization Form

SECTION IX: PROTECTION OF RESEARCH SUBJECTS
--

1. **Risks:** Describe the reasonably foreseeable risks, including risks to subject privacy, discomforts, or inconveniences associated with subjects participating in the research.

Psychological risks are minimal and not different from those of equivalent non-study psychotherapeutic interventions.

Computer-based interventions have been used safely in multiple investigations with a range of populations, and we are unaware of any reported risks associated with these interventions.

The data collected from interviews and self-report forms, as well as urine and breath collection, carry minimal risk. Since the project is taking place in a church setting, there is the possible risk of loss of confidentiality. Every effort will be made to keep information confidential; however, this cannot be guaranteed. Further, only the research team will have access to the results of the drug and alcohol tests. The church based health advisors will not see this information.

2. **Minimizing Risks:** Describe the manner in which the above-mentioned risks will be minimized.
 The Project Coordinator will supervise the participants' use and understanding of the program closely, and research staff will be available to monitor participants' reactions to the program and to answer any clinical issues.

The web-based intervention is highly secure (annual Security Design Review by Yale Information Technology Services is required). The program does not collect any PHI or specific information regarding recent drug use or illegal activities.

3. **Data and Safety Monitoring Plan:** Include an appropriate Data and Safety Monitoring Plan (DSMP) based on the investigator's risk assessment stated below. (Note: the HIC will make the final determination of the risk to subjects.) For more information, see the Instructions, page 24.
- a. What is the investigator's assessment of the overall risk level for subjects participating in this study? Minimal
- b. If children are involved, what is the investigator's assessment of the overall risk level for the children participating in this study? N/A

HIC# 2000022733

- c. Copy, paste, and then tailor an appropriate Data and Safety Monitoring Plan from <http://www.yale.edu/hrpp/forms-templates/biomedical.html> for
 - i. Minimal risk
 - ii. Greater than minimal/moderate risk
 - iii. High risk
- d. For multi-site studies for which the Yale PI serves as the lead investigator:
 - i. How will adverse events and unanticipated problems involving risks to subjects or others be reported, reviewed and managed?
 - ii. What provisions are in place for management of interim results?
 - iii. What will the multi-site process be for protocol modifications?

Overall level of risk for participants is minimal given the nature of this project and procedures in place for careful identification of potential subjects, informed consent process, and protection of confidentiality. We have used the CBT4CBT program successfully and safely in multiple previous trials {[name], 2008 #10267; [name], 2009 #10266; [name], 2014 #11309}.

A Data and Safety Monitoring Board (DSMB) will monitor this project because this population might be considered vulnerable due to their substance use. This board is already in place for the Yale Psychotherapy Development Center ([name], Faculty Advisor). The DSMB is composed of Yale investigators who are independent of the proposed trial and experienced in various aspects of the conduct of clinical trials for the treatment of addictive disorders. We have developed a standard DSMB report form that is used in all Center related trials that summarizes, *on a quarterly basis*:

1. Recruitment, retention, and follow-up rates for the study and compares them to target rates.
2. Rates of data completeness and availability of primary outcome data.
3. Occurrence of AEs and SAEs.
4. Report of study progress since the last report.
5. Rates of recruitment of women, minorities, and children with respect to targets.

These reports are generated by the Data Manager each quarter and signed by each study PI prior to their submission to the DSMB. DSMB comments are documented and forwarded to the Yale IRB at the time of the annual review and re-approval.

Because the projected effect sizes may not be large enough for detection during interim analyses, we are not proposing a preliminary analysis of accumulating efficacy and safety data by treatment. Instead, we propose to submit a quarterly report of aggregate data to the DSMB members that contains screening data, baseline demographics, retention data, serious adverse events data, as well as accrual status including projections, times to milestones, and any other data that will help in the assessment of the clinical trial. Based on this report, each DSMB member will complete a form making one of two recommendations: 1) continue recruitment as planned; or 2) schedule formal DSMB meeting immediately. If any DSMB member recommends a meeting, this will be scheduled within one week, minutes will be kept, the report will be reviewed with the PI, and the committee will vote on whether the study should: 1) continue recruitment unchanged; 2) continue with a protocol amendment; 3) stop recruiting pending further investigation. If, after this meeting, any DSMB member votes to stop recruitment or requests a protocol modification, the Yale IRB will be informed.

HIC# 2000022733

Participants who experience a significant psychiatric or medical problem requiring an overnight hospitalization at an acute care facility will be considered to have experienced an SAE. In general, most SAEs will result in inpatient care and thus in transfer to the inpatient division of CMHC or YNHH. All SAEs will result in the completion of an SAE Form and a verbal report within one hour to the Principal Investigator ([name]). Within 24 hours, the following additional individuals will be informed: 1) All co-investigators; and 2) the DSMB. Adverse events that are serious and unanticipated and probably, possibly, or definitely related or adverse events occurring with greater frequency than anticipated will be reported to the Yale Human Investigation Committee within 5 days of discovery. The procedures for SAE reporting include written documentation using the clinical notes related to the adverse event and specific forms detailing the event with a sign-off by all appropriate supervisory personnel. Communication of recommendations and decisions from all parties (DSMB, Yale Human Investigations Committee, and CMHC Administration) are made back to the investigator in a timely manner. We will report all protocol amendments or changes in the informed consent form to NIDA as well as any temporary or permanent suspension of patient accrual.

4. Confidentiality & Security of Data:

a. What protected health information (medical information along with the HIPAA identifiers) about subjects will be collected and used for the research?

PHI that will be collected includes names, addresses, phone numbers, and email addresses for locator purposes.

Our study assessments/forms have been designed to avoid collecting identifiable information (e.g., no PHI identifiers are collected on CRFs). The only dates collected are protocol session dates. These are changed to ‘number of sessions completed’ when data sets are anonymized and released to other investigators.

b. How will the research data be collected, recorded and stored?

Research data are collected on CRFs and in Qualtrics, and sent to data managers in our research offices on a closed secure network. All computers used by research staff are password protected. No identifying information is on CRFs. Only authorized individuals will have access to CRFs.

c. How will the digital data be stored? CD DVD Flash Drive Portable Hard Drive Secured Server Laptop Computer Desktop Computer Other

d. What methods and procedures will be used to safeguard the confidentiality and security of the identifiable study data and the storage media indicated above during and after the subject’s participation in the study?

Do all portable devices contain encryption software? Yes No

If no, see <http://hipaa.yale.edu/guidance/policy.html>

Confidentiality in regards to collected materials will be maintained via a numbered reference system maintained by the Project Coordinator. Participants’ names will appear only on the consent form, and “key” form kept by the Project Coordinator. The key form linking subject names to ID codes will be stored in a separate, locked file cabinet. Data are stored at our secure data management center; data sets do not include identifying information.

In addition, we have designed all of our CBT4CBT websites such that no sensitive information (i.e., information on illegal behavior) or PHI is collected or stored by the website (including IP address). Moreover, to avoid participants inadvertently revealing sensitive

HIC# 2000022733

information, the website does not use any 'blank fills', and the program shuts down after 10 minutes of inactivity.

- e. What will be done with the data when the research is completed? Are there plans to destroy the identifiable data? If yes, describe how, by whom and when identifiers will be destroyed. If no, describe how the data and/or identifiers will be secured.

Paper copies of participant records containing ID numbers will be moved to Iron Mountain Archives. Source files with subject names will be stored in the regulatory coordinator's office separately under triple lock (building entry, office entry, separate locked file cabinet designated for name files only). The paper log linking subject names to ID codes will be stored in a separate, locked file in the regulatory coordinator's office. The link to the subjects personal information will be kept for the 1 year follow up period after which time the link will be destroyed and the data will become anonymous. The data will be kept in this anonymous form for a minimum of 3 years after the study has ended and then will be destroyed. At the end of the required record retention period, data will be destroyed in accordance with Yale ITS policies 1609 and 1609PR.01. Source data are generally destroyed 3 years after completion of the study at a secure location (Iron Mountain) or by Shred-It.

- f. Who will have access to the protected health information (such as the research sponsor, the investigator, the research staff, all research monitors, FDA, QUACS, SSC, etc.)? (please distinguish between PHI and de-identified data)

The Yale PI and the research staff will have access to PHI and coded data. The funding agency, NIDA, may access the data for routine audits.

- g. If appropriate, has a [Certificate of Confidentiality](#) been obtained?

Obtained

- h. Are any of the study procedures likely to yield information subject to mandatory reporting requirements? (e.g. HIV testing – reporting of communicable diseases; parent interview -incidents of child abuse, elderly abuse, etc.). Please verify to whom such instances will need to be reported.

Limits to confidentiality include only disclosure of acute suicidality, homicidality, or abuse of a minor/elder, as is standard in clinical practice and indicated in the consent form. When there is reasonable cause to suspect or believe there is a case of child abuse or elder abuse, a report will be made to the CT Department of Children and Families (DCF) or CT Department of Social Services (DSS), Protective Services for the Elderly (PSE). Designated clinic personnel will be notified as per clinic policies.

6/29/2011SECTION X: POTENTIAL BENEFITS

Potential Benefits: Identify any benefits that may be reasonably expected to result from the research, either to the subject(s) or to society at large. (Payment of subjects is not considered a benefit in this context of the risk benefit assessment.)

The major potential benefit in this study is in reduction of substance use via the study treatments and affirmation of self-identity and spirituality, which may, in turn, foster improvement in participants' legal, medical, interpersonal, psychological and occupational functioning.

SECTION XI: RESEARCH ALTERNATIVES AND ECONOMIC CONSIDERATIONS

1. **Alternatives:** What other alternatives are available to the study subjects outside of the research?
Individuals who do not wish to participate or who are ineligible for the trial will be given information about substance abuse clinics and mental health centers in the area.

2. **Payments for Participation (Economic Considerations):** Describe any payments that will be made to subjects, the amount and schedule of payments, and the conditions for receiving this compensation.

BSUD subjects will be compensated for time required to complete screening assessments at \$20, baseline assessment at \$20, week 4 assessments at \$10, study assessments at \$10 for each weekly module time point; \$50 for completing all modules, and \$50 at post-treatment for a possible total of \$230.

CHA subjects will be paid \$14.25 per hour by check for the time participated in the project, including time spent in the confidentiality and addiction trainings led by [name], as well as the qualitative interviews. The research team anticipates approximately 86 hours of time in the project, over an 8-12 week time period, for a total of \$1,225.50 paid by check.

3. **Costs for Participation (Economic Considerations):** Clearly describe the subject's costs associated with participation in the research, and the interventions or procedures of the study that will be provided at no cost to subjects.

There will be no costs to subjects associated with participation in this study. Subjects will not be charged for study treatments or evaluations they receive at the clinic.

4. **In Case of Injury:** This section is required for any research involving more than minimal risk.
 - a. Will medical treatment be available if research-related injury occurs?
 - b. Where and from whom may treatment be obtained?
 - c. Are there any limits to the treatment being provided?
 - d. Who will pay for this treatment?
 - e. How will the medical treatment be accessed by subjects?

Because we are evaluating standard behavioral approaches with strong empirical support and no known adverse consequences, study related injuries are expected to be extremely rare. There will be no compensation and/or medical treatment available if injury occurs. Participants or their insurance carrier will be expected to cover costs of any medical treatment.

LITERATURE CITED

REFERENCES

1. Satcher D. Mental Health: Culture, Race, and Ethnicity—A Supplement to Mental Health: A Report of the Surgeon General. 2001. <http://www.ncbi.nlm.nih.gov/books/NBK44243>. Accessed June 25, 2016.
2. National Institute on Drug Abuse. Drug Use Among Racial/Ethnic Minorities. NIH Publication No. 03-3888, Printed 1995, Revised September 1998. Revised 2003.
3. Galvan FH and Caetano R. Alcohol use and Related problems among ethnic minorities in the United States. *Alcohol Res Health*. 2003;27(1):87-94.

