3. **Research Plan:** Summarize the study design and research procedures using non-technical language that can be readily understood by someone outside the discipline. Be sure to distinguish between standard of care vs. research procedures when applicable, and include any flowcharts of visits specifying their individual times and lengths.

B. METHODOLOGY

B.1.a. Recruitment of BSUD:

Forty Black adults, 20 male and 20 female participants, who self-identify as Black and want help with drug and/or alcohol problems in the church setting, will be recruited from within the church itself, Dixwell Avenue Congregational UCC and the two predominately Black neighborhoods in New Haven, CT, Dixwell and Newhallville, immediately surrounding the church. Given past successes with the needs assessment study, using targeted recruitment strategies, including culturally normative flyers disseminated by Black church clergy, online and print ads in Black church bulletins, and culturally sensitive ads on urban radio stations, these same tools will be utilized to recruit the research participants for the pilot project. Participants will be screened by research staff using the DSM-5 Substance Use Criterion to ensure all potential participants meet criteria for a SUD as defined by DSM 5. Inclusion criteria: (1) at least 18 years of age (2) has at least one SUD diagnosis as defined by the DSM 5 (3) self-identified with having a SUD and confirmed after DSM 5 criterion checklist; Exclusion criteria: (1) inability to provide informed

HIC# 2000022733

consent or participate in the study procedures as proposed in the consent (2) active suicidal or homicidal ideation and (3) current engagement in substance abuse treatment.

B.1.b. Recruitment of Church Based Health Advisors (CHAs):

Community partner, [name]--pastor of Dixwell Avenue Congregational United Church of Christ, will advertise the role of the CHA (CHA description in attached documents) in the church bulletin, through church meetings, and by peer nomination, in order to identify church leaders interested in this role. All CHAs must be a member of a Black church in the targeted Newhallville/Dixwell neighborhoods, be at least 18 yo, and have the ability to read and write. It would be preferable, but not necessary, if a CHA had lived experience with drug and/or alcohol use. 12 CHAs will be recruited in total, 10 consistent leaders, and 2 alternates for emergency/unplanned absences.

B.2. Procedure:

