A total of 5 cohorts, each with 8 participants, will meet at Dixwell church on pre-determined days to take the intervention (CBT4CBT) online, simultaneously. Participants in each cohort will complete each online module at their own speed, but meet together on a weekly basis for a total of 8 sessions (8 weeks). Tablets, Wi-Fi hot spots and internet service, will be purchased for the church and made available to participants during the 8 weekly sessions, in addition to allocated times, for review of immediate session topics after each week of a CBT module.

The ten church staff members, known as CHAs, will undergo the informed consent process to participate in the research program, along with two extensive, 8-hour training days, including, but not limited to, topics such as the modules of CBT4CBT, basic research principles, and foundational knowledge related to addiction and drug and alcohol treatment. The CHAs, will then meet together to identify religious practices that can be coupled with each CBT4CBT module, to reinforce lessons taught in each respective module. Two CHAs will be assigned to each cohort, and will meet the 8 participants on a weekly basis, with a back-up CHA also assigned, for emergency/unplanned absences, to ensure each cohort has at least 2 CHA present. All religious practices will be led by the CHA, with any spiritual insights from participants reframed by the CHA, to reinforce lessons from a CBT4CBT module.

A member of the research team will also be present during all CBT4CBT sessions to collaborate with research participants and CHAs. **Table 1**, included below provides a detailed outline of the CBT4CBT modules and approximated spiritual practices to accompany each module. Final practices to accompany each CBT module will be pre-determined by the CHAs.

Table 1. CBT4CBT Intervention Topics

Every Session (led by CHA)	*Check-in, Opening Prayer, Scripture Reading, Praise & Worship (2 song selections) Testimony (optional), Ending Prayer *The proposed agenda above will be modified based on input from CHA.
Session 1	Recognize the Triggers -items that trigger substance use
Session 2	Coping with Craving -skills & tools to deal with cravings
Session 3	Plan Don't Panic -identifying problems in advance & coming up with solutions
Session 4	Go Against the Flow -learning how to make safer decisions
Session 5	Stand up for Yourself -learning how to be assertive & stand up for yourself
Session 6	Stop and Think -challenging negative thoughts

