|  Decisionally Impaired |  Employees |  Pregnant women and/or fetuses |
|  Yale Students |  Females of childbearing potential | |

HIC# 2000022733

NOTE: Is this research proposal designed to enroll children who are wards of the state as potential subjects? Yes No (If yes, see Instructions section VII #4 for further requirements)

3. Inclusion/Exclusion Criteria for BSUD: What are the criteria used to determine subject inclusion or exclusion?

Inclusion criteria:

1. At least 18 years of age
2. Has at least one SUD diagnosis as defined by the DSM 5

Individuals will be excluded who:

1. Are unable provide informed consent or participate in the study procedures as proposed in the consent
2. Active suicidal or homicidal ideation
3. Current engagement in substance abuse treatment
4. Have a current legal case pending, such that incarceration during the 8 week protocol is likely
5. Are in need of detoxification from alcohol, opioids or benzodiazepines

Inclusion/Exclusion for CHAs:

1. At least 18 years of age
2. Membership in church in Newhallville/Dixwell neighborhoods
3. Are able to read and write

4. How will **eligibility be determined, and by whom?**

Individuals (both BSUD and CHAs) who indicate they are interested in hearing more about the study will be offered a meeting with research staff who will provide a brief overview of the protocol and continue the informed consent process. After written or verbal informed consent has been obtained* and a quiz successfully completed, screening assessments will be completed to determine eligibility. *CHAs will need to complete the informed consent process only, and will not need to complete a quiz, nor complete screening assessments.

5. Indicate recruitment methods below. Attach copies of any recruitment materials that will be used.

- | | | |
|--|--|---|
|  Flyers |  Internet/Web Postings |  Radio |
|  Posters |  Mass E-mail Solicitation |  Telephone |
|  Letter |  Departmental/Center Website |  Television |

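### Do the two eligibility lists in the protocol (three exclusions in Section V.3 B.1.a, five in Section VII.3) leave it open who may be enrolled?

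*Protocol*

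**What the plan says.** Eligibility for the participants with substance use disorder is set out in two places in the protocol.

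- **Section V.3, B.1.a (recruitment).** Inclusions: adult age, at least one DSM-5 substance use disorder, and "3) self-identified with having a SUD and confirmed after DSM 5 criterion checklist". Exclusions: inability to consent or take part, followed by "2) active suicidal or homicidal ideation and (3) current engagement in substance abuse treatment". The form's instruction for Section V.3 is to "Summarize the study design and research procedures using non-technical language".
- **Section VII.3 (inclusion/exclusion criteria).** The form asks here: "What are the criteria used to determine subject inclusion or exclusion". Inclusions: adult age and a DSM-5 diagnosis. Exclusions: the same three as in B.1.a, then "Have a current legal case pending, such that incarceration during the 8 week protocol is likely" and "Are in need of detoxification from alcohol, opioids or benzodiazepines".

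Section VII.4 says that screening assessments after consent settle eligibility, and Table 2 lists an inclusion/exclusion interview done by the research assistant at screening. Neither refers to one list or the other. The SAP plans a CONSORT diagram that starts at screening.

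**The concern.** B.1.a reads as a complete numbered list, with no pointer to Section VII.3 and no wording to show that it is partial. Taken alone, it would let in a person facing likely incarceration or needing detoxification, both of whom Section VII.3 bars. It also carries an inclusion that Section VII.3 lacks, so it is not simply an abridged copy.

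Three things could be at stake:

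- **Safety at entry.** None of the three shared exclusions clearly covers need of detoxification.
- **Completion.** Participants "meet together on a weekly basis for a total of 8 sessions (8 weeks", so someone likely to be incarcerated during that time threatens the feasibility criterion.
- **The recruitment result.** The ineligible count in the CONSORT diagram depends on which criteria were applied, and recruitment is part of Aim 1.

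**Working it through.** **Item-by-item comparison**

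| Item | B.1.a | VII.3 |
|---|---|---|
| Inclusion: adult age | yes | yes |
| Inclusion: DSM-5 diagnosis | yes | yes |
| Inclusion: self-identified disorder, checklist-confirmed | yes | no |
| Exclusion: cannot consent or take part | yes | yes |
| Exclusion: suicidal or homicidal ideation | yes | yes |
| Exclusion: already in treatment | yes | yes |
| Exclusion: likely incarceration | no | yes |
| Exclusion: need of detoxification | no | yes |

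Inclusions: 3 − 2 = 1 found only in B.1.a. Exclusions: 5 − 3 = 2 found only in Section VII.3. All items together: 2 + 1 = 3 inclusions and 3 + 2 = 5 exclusions.

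**Is there a contradiction?** Two lists contradict each other if obeying one means breaking the other. Here no item permits what another forbids. A person who passes all eight items satisfies both sections, and a person who fails any item is barred by at least one. The problem arises only if B.1.a is used and the dedicated eligibility item is ignored.

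**How much does the extra inclusion add?** Its checklist half repeats the DSM-5 diagnosis. Its self-identification half is close, though not identical, to the description in Sections VII.1 and VII.6.a of people seeking help with drug or alcohol problems. Nothing in the documents suggests that anyone's eligibility would turn on it.

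**Is B.1.a meant to be exhaustive?** Self-identifying as Black defines the study population, yet it is a numbered item in neither list. It stands in the recruitment text of B.1.a and in Sections VII.1 and VII.6.a. Requirements are therefore spread across the application form, and numbering alone does not make a list complete.

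**Does the telephone or email screen show that the shorter list is in use?** Section VII.7 records only positive DSM-5 responses as health information at that step. That entry answers a privacy question about what is retained. It also omits suicidal ideation and current treatment, which both lists contain, so it cannot show which list is applied.

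**Effect on the completion criterion.** Section V.5 sets 2/3 × 40 = 26.67, rounded up to 27, which is 27/40 = 67.5% and leaves 40 − 27 = 13 non-completers. Someone enrolled despite likely incarceration who then dropped out would use one of those 13, but so would any other non-completer. The arithmetic says nothing specific about the mismatch, and the documents give no frequency for either added exclusion. Likely incarceration is also partly covered by a shared exclusion: "Are unable provide informed consent or participate in the study procedures as proposed in the consent".

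**The case for a change.** The best case for acting is that a summary may drop criteria but should not add one. Neither list contains the other, so precedence has to be inferred. Section II expects 60 people to sign consent and 40 to receive some or all of the intervention, a gap of 60 − 40 = 20. Because eligibility is settled after consent, some of those 20 may be screen failures, and the planners of a later randomized trial would want to know on what criteria. Need of detoxification has no clear equivalent among the shared exclusions, and Section IX.3 rests its minimal-risk rating partly on careful identification of participants. Aligning the two sections would cost almost nothing.

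The mismatch and the missing precedence statement stand, and so does the point about detoxification as a matter of wording. What does not follow is an effect on the trial. The argument needs the shorter list to have been used at screening, and no section shows that it was. The Table 2 screening form, which would decide the matter, is not among the documents and may carry all five exclusions. Low cost alone does not show that a change would alter who is enrolled or what is concluded. Interpreting the CONSORT counts is ordinary reporting: whoever draws the diagram gives reasons for ineligibility and so names the criteria used.

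**Conclusion.** The two lists differ by two exclusions and one inclusion, but they are compatible. The whole protocol, read together, already bars the people the concern is about. This is a clerical inconsistency between a summary section and the dedicated eligibility item, with no demonstrated effect on enrolment, safety or the 27-of-40 criterion. The size of any effect cannot be computed from the documents and may be zero.

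The conclusion assumes that screening staff worked from the protocol as a whole, or from a form built on it. A screening form carrying only the three B.1.a exclusions would change the assessment, but nothing in the documents points to one. The planned period was March 2018 to March 2019, and the SAP dated 12/3/2020 speaks of the study as already implemented, so rewording the protocol now would probably change nothing. Reconciling the two passages is an editorial matter that the usual description of ineligible people beside the CONSORT diagram can handle. No view is taken here on which criteria are clinically right.
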